#### **4.4.2 Timing of Dose Administration**

Trial treatment should be administered on Day 1 of each cycle after all procedures/assessments have been completed as detailed on the Trial Flow Chart (Section 6.0). Trial treatment may be administered up to 3 days before or after the scheduled Day 1 of each cycle due to administrative reasons.

All trial treatments will be administered on an outpatient basis at MDACC.

Pembrolizumab 200 mg will be administered as a 30 minute IV infusion every 3 weeks for up to 2 years

Sites should make every effort to target infusion timing to be as close to 30 minutes as possible. However, given the variability of infusion pumps from site to site, a window of -5 minutes and +10 minutes is permitted (i.e., infusion time is 30 minutes: -5 min/+10 min).

The Pharmacy Manual contains specific instructions for the preparation of the pembrolizumab infusion fluid and administration of infusion solution.

#### **4.4.3 Trial Blinding/Masking**

This is an open-label trial; therefore, the Sponsor, investigator and subject will know the treatment administered.

#### **4.4.4 Radiation Therapy**

##### **4.4.4.1 Suggested Simulation Procedure**

Prior to radiation, we suggest that patients undergo a renal scan and baseline creatinine, to assess potential toxicity to the ipsilateral kidney. Patients will undergo CT simulation in the Department of Radiation oncology. Immobilization will occur with a vac-loc cradle and the arms above the head. 4D CT images will be obtained to assess for respiratory motion, and will scan from the lung apex to approximately L2 inferiorly. Wiring the scars and drain sites with bolus is optional. If bolus is used, we suggest 0.5 cm thickness and 3.5 cm in diameter. Treatment will be planned using IMRT or IMPT and delivered with image-guided radiation therapy (IGRT).

##### **4.4.4.2 Suggested Target Delineation**

##### **Cohort 1 – Hemithoracic Radiation Therapy**

For patients with no gross residual disease, above the level of the diaphragm the planning target volume (PTV) will encompass the ipsilateral external pleura using a “rind” volume, including an 8 mm inner margin (PTV\_inner) and 1-1.5 cm outer margin (PTV\_outer). The outer margin will should be extended lateral to the ribs, with approximately a 0.5 cm margin. Non-enhancing nodal beds will not be contoured or treated. Below the level of the diaphragm, the PTV will encompass only a single crescent-shaped contour with will be named the PTV\_outer. If bolus is placed, the target volume should extend towards the surface and encompass the region of the bolus.

##### **Cohort 2 – Non-Hemithoracic Radiation Therapy**

The gross disease, as delineated on the PET/CT scan and/or the CT scan with contrast, will be contoured as the GTV. A 0.5-1 cm margin will be defined as the CTV, and another 0.5 cm margin will be placed as the PTV if daily kV imaging is performed.

#### **4.4.4.3 Treatment Planning and Prescription Dose**

##### **Cohort 1 – Hemithoracic Radiation Therapy**

Patients will be prescribed a prescription dose of 45 Gy in 25 fractions to the PTV, and 2.4 Gy x 25 fractions to the GTV (if applicable) using a simultaneous integrated boost. Either IMRT or IMPT will be utilized, using techniques described in prior publications from our institutions [15, 18].

##### **Cohort 2 – Non-Hemithoracic Radiation Therapy**

Patients will be treated to one of the following prescribed doses: a) 3 Gy x 10 fractions = 30 Gy, b) 4 Gy x 5 fractions = 20 Gy, c) 5 Gy x 5 fractions = 25 Gy, or d) 45-52.5 Gy in 15 fractions. Patients will be treated using either IMRT or 3D conformal therapy.

#### **4.4.4.4 – Radiation Dose Constraints – Both Cohorts**

*Required Dose Constraints* – Patients are required to meet the following dose constraints: 1) Normal Tissue Complication Probability (NTCP) of the lung <25%, calculated with the Lyman-Kutcher-Berman model [19]. 2) At least 93% of the contralateral lung must receive less than 20 Gy (V20<7%). 3) Maximum spinal cord dose of <50 Gy.

*Suggested Dose Constraints* – We suggest the following dose constraints: 1) At least 50% of heart receive less than 30 Gy, 2) At least 50% of the liver receive less than 30 Gy. 3) Mean dose to stomach (not PTV)<30 Gy, 4) Maximum bowel dose<55 Gy, 5) Kidney V18≤50%.

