**Additional Inclusion Criteria – Cohort 2**

1. Patients must be assessed to be a suitable candidate for radiation therapy by the treating radiation oncologist. Patients that do not meet the dose constraints outlined below will be removed from the study prior to radiation therapy.
2. Any prior number of prior therapies, including prior immunotherapy, is allowed.

3. Patient has received prior treatment with a platinum-pemetrexed regimen.

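### The single required cord maximum of <50 Gy is a biologically looser limit for Cohort 2's 15-fraction option than for 25-fraction plans

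*Combined protocol and SAP*

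**What the plan says.** Section 4.4.4.4 is titled "Radiation Dose Constraints – Both Cohorts". Its first list is mandatory: "Patients are required to meet the following dose constraints". Two of the three items concern lung; the third is "Maximum spinal cord dose of <50 Gy". It carries no qualifier for fraction size, fraction number or equivalent dose, and no other section limits cord dose.

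The schedules are in section 4.4.4.3. Cohort 1 receives "45 Gy in 25 fractions to the PTV", with an optional boost in the same 25 fractions. Cohort 2 has four options: 30 Gy in 10 fractions, 20 Gy in 5, 25 Gy in 5, and "d) 45-52.5 Gy in 15 fractions".

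Under the additional inclusion criteria for Cohort 2 in section 4.3.2, the constraints decide who stays in the trial: "Patients that do not meet the dose constraints outlined below will be removed from the study prior to radiation therapy". Section 4.4.4.2 describes the Cohort 2 target as gross disease plus two margins: "A 0.5-1 cm margin will be defined as the CTV, and another 0.5 cm margin will be placed as the PTV", the second conditional on daily kV imaging.

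**The concern.** The biological effect of a physical dose on late-responding tissue depends on the dose per fraction. A maximum of 50 Gy means 2.0 Gy per fraction over 25 fractions but 3.33 Gy per fraction over 15. Read literally, the rule lets a 15-fraction plan carry a biologically larger cord dose than it allows a 25-fraction plan.

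This is the only written cord limit. The treating radiation oncologist's judgement of suitability is a separate entry requirement with no number attached. The primary objective is safety, so a required organ limit should mean the same thing on every schedule the trial permits.

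**Working it through.** **Inputs from the documents.** Cord limit <50 Gy, both cohorts (4.4.4.4). Cohort 1: 45 Gy in 25 fractions. Cohort 2 options: 30 Gy/10, 20 Gy/5, 25 Gy/5, and 45-52.5 Gy/15 (option d) (4.4.4.3).

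**Assumption.** The documents give no alpha/beta for cord. I use 2-3 Gy, with 1-4 Gy as a sensitivity range.

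**Nothing to reproduce.** The 50 Gy limit is stated, not derived. The protocol's dose arithmetic is correct: 3 × 10 = 30, 4 × 5 = 20, 5 × 5 = 25.

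**Step 1. Convert to 2-Gy fractions.** For total dose D in n fractions, EQD2 = D(D/n + ab)/(2 + ab), where ab is alpha/beta. For example, 45 Gy/15 at ab = 2 gives 45 × (3 + 2)/4 = 56.25 Gy.

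| Cord dose | Gy per fraction | ab 1 | ab 2 | ab 3 | ab 4 |
|---|---|---|---|---|---|
| 50 Gy in 25 (limit) | 2.00 | 50.0 | 50.0 | 50.0 | 50.0 |
| 45 Gy in 15 (full prescription) | 3.00 | 60.0 | 56.3 | 54.0 | 52.5 |
| 50 Gy in 15 (limit) | 3.33 | 72.2 | 66.7 | 63.3 | 61.1 |

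Against 50 Gy, the second row is 8-12.5% higher at ab 3-2 (5-20% over 4-1). The third is 27-33% higher (22-44%) and is an upper bound, because the rule requires less than 50 Gy.

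**Step 2. Dependence on the assumption.** 50 Gy in 15 fractions exceeds 50 Gy in 25 for any finite positive ab, because 3.33 > 2. The 45 Gy/15 comparison needs 45(3 + ab) > 50(2 + ab), so 35 > 5ab, or ab < 7.

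**Step 3. Where the upper bound can arise.** 50/45 = 111%, 50/50 = 100% and 50/52.5 = 95%. A cord just under 50 Gy is therefore possible across the whole option d range: with a hot spot approaching 111% of a 45 Gy prescription, at full dose near 50 Gy, or at about 95% of 52.5 Gy. For prescriptions from 45 to just under 50 Gy, which is 5 of the 7.5 Gy range, a cord at 100% of prescription passes.

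**Step 4. Matched 15-fraction dose.** Setting EQD2 = 50 and solving gives D = 7.5(-ab + √(ab² + 4 × 50 × (2 + ab)/15)), which is 40.5, 41.8, 42.7 and 43.5 Gy for ab 1, 2, 3 and 4. All lie below the lowest option d prescription. At ab 2-3 the matched dose is 93-95% of 45 Gy and 80-81% of 52.5 Gy.

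**Step 5. The other Cohort 2 options.** At full prescription and ab 2/3, 30 Gy/10 is 37.5/36.0 Gy, 20 Gy/5 is 30.0/28.0 Gy and 25 Gy/5 is 43.8/40.0 Gy, all below 50. At ab 1, 25 Gy/5 is exactly 50.0 Gy. Matched doses at ab 2-3 are 35.8-37.2 Gy in 10 fractions and 27.0-28.6 Gy in 5. Only a cord hot spot of at least 27.0/25 = 108% of the 25 Gy prescription, or 35.8/30 = 119% of the 30 Gy prescription, would reach them.

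**Step 6. Geometry.** The Cohort 2 margins total 0.5-1 cm + 0.5 cm = 1-1.5 cm, so the cord doses above need disease close to the cord.

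**The case against.** **The benchmark is not the protocol's.** Section 4.4.4.4 does not say that 50 Gy means 50 Gy in 25 fractions, or that an equivalent dose of 50 Gy is the ceiling. Any physical-dose limit loosens as fractions get larger. This stands, and it confines the point to inconsistency. A reader might infer that the protocol permits an unsafe cord dose. The documents do not support that: they give no cord tolerance and do not say how 50 Gy was chosen.

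**Passing at full prescription is not peculiar to option d.** A reader might take it as such, but a cord at the full 45 Gy in 25 fractions also passes, as do the other three Cohort 2 options. What sets option d apart is that full prescription passes while exceeding the equivalent of 50 Gy in 25 fractions; 45 Gy/25 is only 42.8-43.2 Gy on that scale. This stands.

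**Exposure is narrow and clinicians have discretion.** Option d is one of four regimens, the margins are small, and a radiation oncologist may well hold the cord lower. This stands as a limit on how many patients are affected, but it does not close the gap, because nothing written requires a lower cord dose.

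**Other limits in the section are physical too.** The contralateral lung, heart, liver, stomach, bowel and kidney limits are also uncorrected physical doses. That is true, and it shows a convention. It does not make the cord limit equivalent across schedules.

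**The replacement value depends on an assumption.** It moves between 40.5 and 43.5 Gy with alpha/beta. That is a reason for radiation oncology to choose and state the value, not for leaving 15-fraction plans on the 25-fraction figure.

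**Conclusion.** The point holds as an inconsistency in a required limit. At alpha/beta 2-3, the rule passes a 15-fraction cord dose equivalent to 54-56 Gy at the full 45 Gy prescription, and up to just under 63-67 Gy anywhere in the option d range, against 50 Gy for a 25-fraction plan at the same limit. The direction at the limit needs only the linear-quadratic model; the sizes rest on the assumed alpha/beta.

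It would go too far to conclude that any patient would be overdosed, or that the upper bound is confined to prescriptions near 52.5 Gy. With no cord doses or regimen mix in the documents, the number of patients affected cannot be estimated and may be none. The point does not touch the primary endpoint definition, stopping rule or sample size. It should be corrected because it concerns patient protection and is cheap to mend. My confidence is medium.

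**What to change.** In section 4.4.4.4, keep <50 Gy for 25-fraction plans and add a separate required cord maximum for 15-fraction plans on the same fractionation-corrected scale. One workable value is at most 41 Gy physical in 15 fractions: 41 × (2.733 + 2)/4 = 48.5 Gy at alpha/beta 2 and 41 × (2.733 + 3)/5 = 47.0 Gy at 3. At alpha/beta 1 it gives 51.0 Gy, so if that value is to be covered the limit should be 40 Gy (48.9 Gy). Radiation oncology should confirm the figure and the protocol should state the alpha/beta used.

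The cost is a wording amendment and one planning check per 15-fraction plan. The downside is that some option d plans may need re-planning or may no longer qualify; the documents do not allow that number to be estimated.

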### **4.5 Randomization or Treatment Allocation**

No randomization will be performed.

### **4.6 Stratification**

No stratification will be done.

### **4.7 Concomitant Medications/Vaccinations (allowed & prohibited)**

Medications or vaccinations specifically prohibited in the exclusion criteria are not allowed during the ongoing trial. If there is a clinical indication for one of these or other medications or vaccinations specifically prohibited during the trial, discontinuation from trial therapy or vaccination may be required. The investigator should discuss any questions regarding this with the Merck Clinical team. The final decision on any supportive therapy or vaccination rests with the investigator and/or the subject's primary physician.

#### **4.7.1 Acceptable Concomitant Medications**

All treatments that the investigator considers necessary for a subject's welfare may be administered at the discretion of the investigator in keeping with the community standards of

medical care. All concomitant medication will be recorded on the case report form (CRF) including all prescription, over-the-counter (OTC), herbal supplements, and IV medications and fluids. If changes occur during the trial period, documentation of drug dosage, frequency, route, and date may also be included on the CRF.

All concomitant medications received within 28 days before the first dose of trial treatment and 30 days after the last dose of trial treatment should be recorded. Concomitant medications administered after 30 days after the last dose of trial treatment should be recorded for SAEs and ECIs as defined in Section 7.2.

### **4.7.2 Prohibited Concomitant Medications**

Subjects are prohibited from receiving the following therapies during the Screening and Treatment Phase (including retreatment for post-complete response relapse) of this trial:

- Antineoplastic systemic chemotherapy or biological therapy
- Immunotherapy not specified in this protocol
- Chemotherapy not specified in this protocol
- Investigational agents other than pembrolizumab
- Radiation therapy
  - Note: Radiation therapy to a symptomatic solitary lesion or to the brain may be allowed at the investigator's discretion.
- Live vaccines within 30 days prior to the first dose of trial treatment and while participating in the trial. Examples of live vaccines include, but are not limited to, the following: measles, mumps, rubella, varicella/zoster, yellow fever, rabies, BCG, and typhoid vaccine.
- Systemic glucocorticoids for any purpose other than to modulate symptoms from an event of clinical interest of suspected immunologic etiology. The use of physiologic doses of corticosteroids may be approved after consultation with Merck.

Subjects who, in the assessment by the investigator, require the use of any of the aforementioned treatments for clinical management should be removed from the trial. Subjects may receive other medications that the investigator deems to be medically necessary.

The Exclusion Criteria describes other medications which are prohibited in this trial.

There are no prohibited therapies during the Post-Treatment Follow-up Phase.

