#### **4.3.3 Subject Exclusion Criteria**

The subject must be excluded from participating in the trial if the subject:

1. Is currently participating and receiving study therapy or has participated in a study of an investigational agent and received study therapy or used an investigational device within 4 weeks of the first dose of treatment.
2. Has a diagnosis of immunodeficiency. Note that patients should not receive steroids during Pembrolizumab administration.
3. Has a known history of active TB (Bacillus Tuberculosis)
4. Hypersensitivity to pembrolizumab or any of its excipients.
5. Has had a prior anti-cancer monoclonal antibody (mAb) within 4 weeks prior to study Day 1 or who has not recovered (i.e.,  $\leq$  Grade 1 or at baseline) from adverse events due to agents administered more than 4 weeks earlier.
6. Has had prior chemotherapy, targeted small molecule therapy, or radiation therapy within 2 weeks prior to study Day 1 and who have not recovered adequately from this treatment ( $\leq$ Grade 2 toxicity at the time of enrollment).
7. Has a known additional malignancy that is progressing or requires active treatment. Patients with a stage I-III cancer that has been cured over two years ago are *not* excluded in the study.
8. Has known active central nervous system (CNS) metastases and/or carcinomatous meningitis. Subjects with previously treated brain metastases may participate provided they are stable (without evidence of progression by imaging for at least four weeks prior to the first dose of trial treatment and any neurologic symptoms have returned to baseline), have no evidence of new or enlarging brain metastases, and are not using steroids for at least 7 days prior to trial treatment. This exception does not include carcinomatous meningitis which is excluded regardless of clinical stability.
9. Has active autoimmune disease that has required systemic treatment in the past 2 years (i.e. with use of disease modifying agents, corticosteroids or immunosuppressive drugs). Replacement therapy (eg., thyroxine, insulin, or physiologic corticosteroid replacement therapy for adrenal or pituitary insufficiency, etc.) is not considered a form of systemic treatment.
10. Has a history of (non-infectious) pneumonitis that required steroids or current pneumonitis.

11. Has an active infection requiring systemic therapy.
12. Has known psychiatric or substance abuse disorders that would interfere with cooperation with the requirements of the trial.

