# Proprietary Information of MD Anderson

2015-0856

Version 23

Page 17

Toxicity	Hold Treatment For Grade	Timing for Restarting Treatment	Discontinue Subject/Off-Study Criteria (“Unacceptable” Toxicities)
Diarrhea/Colitis	2-3	Toxicity resolves to Grade 0-1.	Toxicity does not resolve within 12 weeks of last dose or inability to reduce corticosteroid to 10 mg or less of prednisone or equivalent per day within 12 weeks.
	4	Permanently discontinue	Permanently discontinue/Off-Study
AST, ALT, or Increased Bilirubin	2	Toxicity resolves to Grade 0-1	Toxicity does not resolve within 12 weeks of last dose.
	3-4	Permanently discontinue (see exceptions below) 	Permanently discontinue/Off-Study
Type 1 diabetes mellitus (if new onset) or Hyperglycemia	T1DM or 3-4	Hold pembrolizumab for new onset Type 1 diabetes mellitus or Grade 3-4 hyperglycemia associated with evidence of beta cell failure.	Resume pembrolizumab when patients are clinically and metabolically stable.
Hypophysitis	2-3	Toxicity resolves to Grade 0-1	Toxicity does not resolve within 12 weeks of last dose or inability to reduce corticosteroid to 10 mg or less of prednisone or equivalent per day within 12 weeks.
	4	Permanently discontinue	Permanently discontinue/Off-Study
Hyperthyroidism	3	Toxicity resolves to Grade 0-1	Toxicity does not resolve within 12 weeks of last dose or inability to reduce corticosteroid to 10 mg or less of prednisone or equivalent per day within 12 weeks.
	4	Permanently discontinue	Permanently discontinue/Off-Study
Hypothyroidism	2-4	Therapy with pembrolizumab can be continued while treatment for the thyroid disorder is instituted	Therapy with pembrolizumab can be continued while treatment for the thyroid disorder is instituted.
Infusion Reaction	3-4	Permanently discontinue	Permanently discontinue/Off-Study
Pneumonitis	2	Toxicity resolves to Grade 0-1	Toxicity does not resolve within 12 weeks of last dose or inability to reduce corticosteroid to 10 mg or less of prednisone or equivalent per day within 12 weeks. Recurrent grade 2 pneumonitis requires discontinuation of pembrolizumab.
	3-4	Permanently discontinue	Permanently discontinue/Off-Study
Renal Failure or Nephritis	2	Toxicity resolves to Grade 0-1	Toxicity does not resolve within 12 weeks of last dose or inability to reduce corticosteroid to 10 mg or less of prednisone or equivalent per day within 12 weeks.
	3-4	Permanently discontinue	Permanently discontinue/Off-Study

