### *Management of Radiation Pneumonitis*

Patients who develop Grade  $\geq 2$  pneumonitis will be managed according to standard clinical guidelines. If supportive measures are unsuccessful, and/or if the symptoms persist despite this approach, steroids and a referral to pulmonary medicine will be considered. A standard regimen of prednisone includes 40-60 mg daily x 2 weeks, then tapering over the next 3-6 weeks based on symptom status. Interventions such as hospitalization, intravenous steroids, and oxygen administration will be performed at the treating physician's discretion.

As noted in the Statistical Considerations section below (Section 8.0), the study will be stopped if 3/6 or 6/12 patients develop Grade 3 or higher radiation pneumonitis. If 0/6, 1/6, or 2/6 patients develop this toxicity, the study will continue. No dose de-escalation will be performed because all patients are already receiving the minimal therapeutic microscopic dose of radiation, and therefore any further reductions in treatment intensity are not likely to control the disease (and still carry the risk of toxicity). Furthermore, our institution does not have experience escalating the radiation dose in mesothelioma higher than that described in this study, and thus it is not appropriate to do so in conjunction with Pembrolizumab without first assessing the effect of higher doses of radiation therapy alone (without immunotherapy). The study is thus addressing the question of whether our institution's current radiation regimen for malignant pleural mesothelioma, in both the unresectable and pleurectomy/decortication settings, is safe with Pembrolizumab. In essence, the two regimens that we are testing are those in the two cohorts that we have included, the first being the most aggressive and including the entire hemithorax (Cohort 1), and the second being a much more limited field and including only the region of palliation (Cohort 2). This trial will provide data as to whether the immunotherapy-radiation combination should be further explored in neither context, only the less aggressive scenario, or in both patient populations.

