## 4.8 Rescue Medications & Supportive Care

### 4.8.1 Supportive Care Guidelines

Subjects should receive appropriate supportive care measures as deemed necessary by the treating investigator. Suggested supportive care measures for the management of adverse events with potential immunologic etiology are outlined below and in greater detail in the ECI guidance document. Where appropriate, these guidelines include the use of oral or intravenous treatment with corticosteroids as well as additional anti-inflammatory agents if symptoms do not improve with administration of corticosteroids. Note that several courses of steroid tapering may be necessary as symptoms may worsen when the steroid dose is decreased. For each disorder, attempts should be made to rule out other causes such as metastatic disease or bacterial or viral infection, which might require additional supportive care. The treatment guidelines are intended to be applied when the investigator determines the events to be related to pembrolizumab.

Note: if after the evaluation the event is determined not to be related, the investigator is instructed to follow the ECI reporting guidance but does not need to follow the treatment guidance (as outlined in the ECI guidance document). Refer to Section 5.2.1 for dose modification.

It may be necessary to perform conditional procedures such as bronchoscopy, endoscopy, or skin photography as part of evaluation of the event. Suggested conditional procedures, as appropriate, can be found in the ECI guidance document.

- **Pneumonitis:**

- For **Grade 2 events**, treat with systemic corticosteroids. When symptoms improve to Grade 1 or less, steroid taper should be started and continued over no less than 4 weeks.
- For **Grade 3-4 events**, immediately treat with intravenous steroids. Administer additional anti-inflammatory measures, as needed.
- Add prophylactic antibiotics for opportunistic infections in the case of prolonged steroid administration.

- **Diarrhea/Colitis:**

Subjects should be carefully monitored for signs and symptoms of enterocolitis (such as diarrhea, abdominal pain, blood or mucus in stool, with or without fever) and of bowel perforation (such as peritoneal signs and ileus).

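### The protocol's rules on steroids for Grade 2 radiation pneumonitis contradict each other, and the SAP does not say how a patient removed for steroid use is counted.

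*Combined protocol and SAP*

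**What the plan says.** **Steroids barred.** Section 4.7.2 lists among the therapies prohibited during screening and treatment "Systemic glucocorticoids for any purpose other than to modulate symptoms from an event of clinical interest of suspected immunologic etiology". Subjects who "require the use of any of the aforementioned treatments for clinical management should be removed from the trial". Exclusion criterion 2 in Section 4.3.3 adds, with no exception: "Note that patients should not receive steroids during Pembrolizumab administration". The opening of Section 4.7 is softer and says that "discontinuation from trial therapy or vaccination may be required".

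**Steroids provided for.** Under Management of Radiation Pneumonitis (Section 4.4.1.2), if supportive measures fail in Grade 2 or higher pneumonitis, "steroids and a referral to pulmonary medicine will be considered". The course is described: "A standard regimen of prednisone includes 40-60 mg daily x 2 weeks, then tapering over the next 3-6 weeks based on symptom status". Section 4.8.1 directs steroids for Grade 2 pneumonitis, but "The treatment guidelines are intended to be applied when the investigator determines the events to be related to pembrolizumab".

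**Counting.** Sections 4.2.3 and 7.2 make the off-study column of Table 3 the primary toxicity endpoint. In the pneumonitis row, Grade 3-4 qualifies at once. Grade 2 leads to a hold. It qualifies later if it has not resolved within 12 weeks of the last dose, or on "inability to reduce corticosteroid to 10 mg or less of prednisone or equivalent per day within 12 weeks". Recurrent Grade 2 requires discontinuation.

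**Leaving the study.** The off-study list in Section 6.1.4.1 does not name steroid use. It calls only one group non-evaluable: patients with Grade 3 or higher toxicity during radiotherapy.

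**The concern.** Radiation pneumonitis is a main risk the protocol names for these patients, and the regimen adds a drug that can also cause pneumonitis. If steroid use for the radiation form means removal, whether a Grade 2 patient stays under assessment depends on which treatment is blamed. Pneumonitis suspected to be immunologic fits the Section 4.7.2 exception; the same picture attributed to radiation does not. Section 6.2.3.2 presumes an immune cause only when no other cause is found, and recent chest radiotherapy offers another cause.

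For Grade 2, every qualifying Table 3 criterion comes after the point at which steroids would start. Removal at that point can break the observation on which the endpoint depends. At stake are the toxicity estimate and a stopping rule that turns on one patient in six.

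**Working it through.** **1. The rules side by side, for Grade 2 pneumonitis after radiotherapy**

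| Place | If attributed to radiation | If suspected immunologic |
|---|---|---|
| 4.4.1.2, radiation pneumonitis | Steroids considered if supportive measures fail | Not addressed |
| 4.8.1 | Does not apply | Steroids directed |
| 4.7.2 | Steroids barred; subject should be removed | Exception applies |
| 4.7 | Discontinuation possible, not mandatory | Same |
| 4.3.3, criterion 2 | No steroids during pembrolizumab | Same |
| Table 3 | Hold, then judge over 12 weeks | Same |
| 6.1.4.1 | Steroid use not an off-study reason | Same |

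The Table 3 row is taken to serve both attributions, because the table's last row is for all other radiation-related toxicity. The described prednisone course lasts 2 + 3 = 5 to 2 + 6 = 8 weeks. In the radiation column, treating under 4.4.1.2 triggers removal under 4.7.2, while Table 3 expects continued assessment.

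**2. What follow-up remains after removal**

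- Adverse events are monitored for 30 days after treatment ends, serious ones for 90 days (Section 4.10).
- Events above Grade 1 are followed to Grade 0-1 or to new anti-neoplastic therapy (Section 6.1.5.3).
- Concomitant medication is recorded to 30 days after the last dose, and later only for serious events and events of clinical interest (Section 4.7.1).

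Persistence or worsening may therefore still be seen. Steroid reduction at 12 weeks may not be recorded, and recurrence on pembrolizumab cannot be observed once the drug has stopped. Section 7.2 calls for summaries on evaluable subjects but does not say whether a patient removed for steroids is one, or is replaced.

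**3. The plan's own stopping figures**

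Inputs from Section 7.2: prior beta(0.6, 1.4), limit 30%, cut-off 0.80, boundaries 3/6 and 6/12. With x events in n patients the posterior is beta(0.6 + x, 1.4 + n − x).

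- 3/6: Pr(rate > 0.30) = 0.800 (0.800003, just over the cut-off), so stop.
- 5/12: 0.772, continue. 6/12: 0.905, stop.

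The stated boundaries reproduce. The exact probability of 3 or more events in 6 at true rates 0.10, 0.20, 0.30, 0.40 and 0.50 is 0.016, 0.099, 0.256, 0.456 and 0.656. Table X gives 0.017, 0.099, 0.254, 0.462 and 0.650 from 1000 simulations, so it reproduces on the first-look basis.

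**4. One uncounted event**

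If one of three events among the first six is not counted and the patient stays in the denominator, the count is 2/6. The posterior is then Pr(rate > 0.30 | beta(2.6, 5.4)) = 0.523, and the cohort continues.

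**5. Sensitivity, on an assumed loss**

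The documents give no rate of Grade 2 pneumonitis. Let f be the assumed share of qualifying patients who go uncounted, and p the true rate. The counted rate is p(1 − f) if they stay in the denominator as non-events, or p(1 − f)/(1 − pf) if they are replaced. For p = 0.40 and f = 25% this gives 0.40 × 0.75 = 0.30, or 0.30/0.90 = 0.333.

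Probability of 3 or more in 6:

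| True rate | f = 0 | f = 10%, kept / replaced | f = 25%, kept / replaced |
|---|---|---|---|
| 0.40 | 0.456 | 0.373 / 0.404 | 0.256 / 0.320 |
| 0.50 | 0.656 | 0.558 / 0.606 | 0.404 / 0.515 |

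These show how the rule responds to a loss. They do not estimate the loss.

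**The case against.** A reader might infer that patients with the trial's key toxicity drop out uncounted. The documents do not support that. Treatment-related Grade 3-4 pneumonitis after radiotherapy is itself a Table 3 off-study criterion, and meeting it is the endpoint (Section 4.2.3). The pneumonitis stopping rule in Section 4.4.1.2 also names Grade 3 or higher. Steroids given afterwards do not undo the count.

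A reader might also infer that a removed Grade 2 patient can never meet a criterion. That goes too far, because Sections 4.10, 6.1.4.1 and 6.1.5.3 all continue some follow-up.

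The trigger is narrow as well. Steroids for radiation pneumonitis come only after supportive measures fail, the exception needs only a suspected immunologic cause, and Section 4.7 leaves the final decision on supportive therapy to the investigator or primary physician. The ban in Section 4.3.3 concerns steroids during pembrolizumab, which Table 3 holds at Grade 2.

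Timing limits the effect further. Section 4.2.3 places the end of monitoring about 3 months, or 13 weeks, after radiotherapy. A criterion 12 weeks after the last dose falls inside that only if the last dose came within about 13 − 12 = 1 week of the end of radiotherapy, while pembrolizumab may start up to 1 month after it. Some late Grade 2 criteria would miss the minimum window even with full retention. Cohort 2's shorter courses leave more room, and Section 7.2 says at least 4 months. This is a separate window question.

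All of this shrinks the effect. None of it removes the contradiction or supplies a counting rule.

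**Conclusion.** The point stands in a limited form. The steroid rules cannot all be followed for Grade 2 pneumonitis attributed to radiation, and the plan does not say how a patient removed for steroid use enters the toxicity count. Such a patient may not be observed to meet, or be counted for, non-resolution, failed steroid reduction, recurrence or worsening. That could bias the toxicity rate downward and make the stopping rule less likely to act; the documents do not show that it will.

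The size is unknown. What is certain is the fragility at the first look: one event separates a posterior of 0.800 from 0.523. A loss large enough to lower the stopping probability materially rests wholly on an assumed f. It needs Grade 2 cases that were attributed to radiation, given steroids, removed, later qualifying within the window, and then missed by the remaining follow-up.

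**What to change.** 1. Reconcile Sections 4.3.3, 4.4.1.2 (radiation pneumonitis), 4.7, 4.7.2 and 6.1.4.1 and Table 3 on whether a patient given steroids for pneumonitis stays on trial. Which clinical rule is right is for the investigators and sponsor; this review does not choose one.

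2. Add to Section 7.2 that any patient removed because pneumonitis of any attribution needed steroids stays in the denominator, is assessed to the end of the toxicity window, and is counted if a Table 3 criterion is met. Steroid use would have to be recorded over the same period, since Section 4.7.1 otherwise stops at 30 days for most events.

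The cost is protocol wording, one SAP sentence and a little more data collection in few patients. The observed toxicity rate may be slightly higher. The boundaries and Table X need no change, since Table X already takes every event as counted.
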